## Safety Set

Panel/Parameter: <parameter>

[1] Baseline = Screening (Day -28 to Day -15); Percentages are based on the number of subjects with a non-missing measurement for that variable in each corresponding visit; N = Number of safety subjects; n = Number of subjects with data in the summarized category

ANCS = Abnormal, not clinically significant; ACS = Abnormal, clinically significant; UE = Un-evaluable

Program location/program name.sas/ddmmmyyyy/hh:mm

Source Data: Listing xxxxxxx Database Extract Date: ddmmmyyyy

---

Programming notes:

Parameter = Blood Glucose, Total Protein, Albumin, Albumin to Globulin Ratio, Serum Cholesterol(total), Serum Triglycerides, Serum Creatinine, Blood Urea Nitrogen(BUN), Sodium, Potassium, Bicarbonate

Repeat table for:

Table 14.3.4.2 'Summary of Potentially Clinically Significant Laboratory Result - Hematology'

Panel/Parameter: <Parameter> (<Units>)

Parameter = Erythrocyte Count, Hemoglobin, Packed Cell Volumne, Activated Partial Thromboplastin Time and Prothrombin Time, Mean Corpuscular Volumne, Mean Corpuscular Hemoglobin, Mean Corpuscular Hemoglobin Concentration, Red Cell Distribution Width, Total Leucocyte Count (absolute and percent), Differential Leucocyte Count (absolute and percent), Platelet Count

Table 14.3.4.3 Summary of Potentially Clinically Significant Laboratory Result - Urinalysis

Panel/Parameter: <Parameter> (<Units>)

Parameter = Color, appearance, pH, Microscopy, Specific gravity, Glucose, Protein, Ketones, Blood, Billirubin, Leukocyte Esterase, Nitrite

Table 14.3.6.2 Summary of Potentially Clinically Significant Vital Signs

Panel/Parameter: <Parameter> (<Units>)

Parameter = Systolic Blood Pressure (mmHg), Diastolic Blood Pressure (mmHg), Pulse rate (beats per minute), Respiratory rate (per minute)

Footnote: [1] Baseline = Day 1 (1hr pre-dose); N = Number of safety subjects; ANCS = Abnormal, not clinically significant;

ACS = Abnormal, clinically significant; UE = Un-evaluable.

Pre-dose = within 1 hour before study drug administration in the morning (prior to pre-dose spirometry and PK procedure) on Day1 (Baseline) and Day14;

Post-dose = within 1 hour after study drug administration in the morning; on Day1 and Day14;

Trough = approximately 24 hours after study drug administration in the morning Day1.

Percentages are based on the number of subjects with a non-missing measurement for that variable in each corresponding visit.

---

Table 14.3.5.1.1  
 Summary of Laboratory Results - Biochemistry

Safety Set

Panel/Parameter: <Parameter> (<Units>)

Visit	Statistic	GSP304				Spiriva R		
		(N=xxx)	(N=xxx)	(N=xxx)	Total (N=xxx)	Placebo (N=xxx)	5 ug (N=xxx)	Total (N=xxx)
Baseline	n	xxx	xxx	xxx	xxx	xxx	xxx	xxx
	Mean (SD)	xx.x (xx.xx)	xx.x (xx.xx)	xx.x (xx.xx)	xx.x (xx.xx)	xx.x (xx.xx)	xx.x (xx.xx)	xx.x (xx.xx)
	Median	xx.x	xx.x	xx.x	xx.x	xx.x	xx.x	xx.x
	Min; Max	xx; xx	xx; xx	xx; xx	xx; xx	xx; xx	xx; xx	xx; xx
Day 7	n	xxx	xxx	xxx	xxx	xxx	xxx	xxx
	Mean (SD)	xx.x (xx.xx)	xx.x (xx.xx)	xx.x (xx.xx)	xx.x (xx.xx)	xx.x (xx.xx)	xx.x (xx.xx)	xx.x (xx.xx)
	Median	xx.x	xx.x	xx.x	xx.x	xx.x	xx.x	xx.x
	Min; Max	xx; xx	xx; xx	xx; xx	xx; xx	xx; xx	xx; xx	xx; xx
Change from Baseline	n	xxx	xxx	xxx	xxx	xxx	xxx	xxx
	Mean (SD)	xx.x (xx.xx)	xx.x (xx.xx)	xx.x (xx.xx)	xx.x (xx.xx)	xx.x (xx.xx)	xx.x (xx.xx)	xx.x (xx.xx)
	Median	xx.x	xx.x	xx.x	xx.x	xx.x	xx.x	xx.x
	Min; Max	xx; xx	xx; xx	xx; xx	xx; xx	xx; xx	xx; xx	xx; xx
Continue for other visits								

[1] Baseline = Screening (Day -28 to Day -15) ; N = Number of safety subjects; n = Number of subjects with data in the summarized category

Program location/program name.sas/ddmmmyyyy/hh:mm

Source Data: Listing xxxxxxx Database Extract Date: ddmmmyyyy

Programming notes:

Refer to SAP section 6.1 for Days

Parameter = Blood Glucose, Total Protein, Albumin, Albumin to Globulin Ratio, Serum Cholesterol (total), Serum Triglycerides, Serum Creatinine, Blood Urea

Nitrogen (BUN), Sodium, Potassium, Bicarbonate, GFR

Parameter= AST(SGOT),ALT(SGPT),Gamma-glutamyl transferase, Alkaline Phosphatase, Total Bilirubin,Direct Bilirubin

Repeat table for:

Table 14.3.5.2.1 'Summary of Laboratory Results - Hematology'

Panel/Parameter: <Parameter> (<Units>)

Parameter = Erythrocyte Count, Hemoglobin, Packed Cell Volume, Activated Partial Thromboplastin Time and Prothrombin Time, Mean Corpuscular Volume, Mean Corpuscular Hemoglobin, Mean Corpuscular Hemoglobin Concentration, Red Cell Distribution Width, Total Leucocyte Count (absolute and percent), Differential Leucocyte Count (absolute and percent), Platelet Count

Table 14.3.6.1 Summary of Vital Signs

Panel/Parameter: <Parameter> (<Units>)

Parameter = Systolic Blood Pressure (mmHg), Diastolic Blood Pressure (mmHg), Pulse rate (beats per minute), Respiratory rate (per minute)  
Change (next day) to (trough)  
Change 'Visit' to 'Visit [1]'

Footnote: [1] Pre-dose = within 1 hour before study drug administration in the morning (prior to pre-dose spirometry and PK procedure) on Day 1 (Baseline) and Day 14; Post-dose = within 1 hour after study drug administration in the morning; on Day 1 and Day 21; Trough = approximately 24 hours after study drug administration in the morning on Day 1

Table 14.3.6.4 Summary of Electrocardiogram Results

Panel/Parameter: <Parameter> (<Units>)

Parameter= Heart Rate (beats/minute), PR(msec), QRS(msec), QTcB(msec), QTcF(msec)

Footnote: [1] Baseline = Day 1 (pre-dose); N = Number of safety subjects;n = Number of subjects with data in the summarized category

Table 14.3.5.1.2  
 Shift Summary from Baseline to Day 21 in Biochemistry

Safety Set

Panel/Treatment Group/Parameter: <Placebo>(<N=xxx>); < Parameter> (<Units>)

Baseline [1]	Number of Subjects			Subject Status at Day 21			
	Baseline	Day 21	Day 21 and Baseline	Normal	Abnormal	ANCS	ACS
	N 1	N 2	N 3	n/N 3 (%)	n/N 3 (%)	n/N 3 (%)	n/N 3 (%)
Total	xx	xx	yy	xx/yy (xx.x) [2]	xx/yy (xx.x)	xx/yy (xx.x)	xx/yy (xx.x)
Normal	xx	xx	yy	xx/yy (xx.x) [3]	xx/yy (xx.x)	xx/yy (xx.x)	xx/yy (xx.x)
Abnormal	xx	xx	yy	xx/yy (xx.x) [4]	xx/yy (xx.x)	xx/yy (xx.x)	xx/yy (xx.x)
ANCS	xx	xx	yy	xx/yy (xx.x)	xx/yy (xx.x)	xx/yy (xx.x)	xx/yy (xx.x)
ACS	xx	xx	yy	xx/yy (xx.x)	xx/yy (xx.x)	xx/yy (xx.x)	xx/yy (xx.x)

[1] Baseline: Screening (Day -28 to Day -15); N1 = Number of safety subjects with baseline data; N2 = Number of safety subjects with Day 21 data; N3 = Number of safety subjects with baseline and Day 21 data; n = Number of subjects with data in the summarized category

Percentages are based on the number of subjects with a non-missing measurement for that variable in each corresponding visit.

[2] Percentages are based on total subjects with baseline and Day 21 data

[3] Percentages are based on subjects with normal status at baseline that have Day 21 data

[4] Percentages are based on subjects with abnormal status at baseline that have Day 21 data; similar for ANCS, ACS.

ANCS = Abnormal, not clinically significant; ACS = Abnormal, clinically significant

program location/program name.sas/ddmmmyyyy/hh:mm

Source Data: Listing xxxxxxx Database Extract Date: ddmmmyyyy

Programming notes:

For each laboratory parameter, subjects are included only once,  
 in the maximum post-baseline severity, for that laboratory parameter.

Subjects without any post-baseline results are not included in the shift summary

Parameter = Blood Glucose, Total Protein, Albumin, Albumin to Globulin Ratio, Serum Cholesterol (total), Serum Triglycerides, Serum Creatinine, Blood Urea Nitrogen (BUN), Sodium, Potassium, Bicarbonate

AST(SGOT), ALT(SGPT), Gamma-glutamyl transferase, Alkaline Phosphatase, Total Bilirubin, Direct Bilirubin,

Repeat this table for

Table 14.3.5.2.2 'Shift Summary from Baseline to Day 21 in Hematology'

Panel/Treatment Group/Parameter: <Placebo>(<n=xxx>); < Parameter> (<Units>)

Parameter = Erythrocyte Count, Hemoglobin, Packed Cell Volumne, Activated Partial Thromboplastin Time and Prothrombin Time, Mean Corpuscular Volumne, Mean Corpuscular Hemoglobin, Mean Corpuscular Hemoglobin Concentration, Red Cell Distribution Width, Total Leucocyte Count (absolute and percents), Differential Leucocyte Count (absolute and percents), Platelet Count

Table 14.3.5.3.2 ' Shift Summary from Baseline to Day 21 in Urinalysis'

Panel/Treatment Group/Parameter: <Placebo>(<n=xxx>); < Parameter> (<Units>)

Parameter=Color, appearance, pH, Microscopy, Specific gravity, Glucose, Protein, Ketones, Blood, Billirubin, Leukocyte Esterase, Nitrite

Table 14.3.6.3 ' Shift Summary from Baseline to Day 21 in Vital Signs'

Panel/Treatment Group/Parameter: <Placebo>(<n=xxx>); < Parameter> (<Units>)

Parameter = Systolic Blood Pressure (mmHg), Diastolic Blood Pressure (mmHg), Pulse rate (beats per minute), Respiratory rate (per minute)

Footnote: [1] Baseline = Day 1 (1hr pre-dose)

Table 14.3.6.6 ' Shift Summary from Baseline to Day 21 in ECG Interpretation '

Panel/Treatment Group/Pl acebo ( <n=xxx>)

Footnote: [1] Baseline = Day 1 (pre-dose)

Table 14.3.5.3.1  
 Summary of Laboratory Results - Urinalysis

Safety Set

Panel/Parameter: <Parameter> (<Units>)

Visit	Category	GSP304				Spiriva R	
		(N=xxx) n (%)	(N=xxx) n (%)	(N=xxx) n (%)	Total (N=xxx) n (%)	Placebo (N=xxx) n (%)	5 ug (N=xxx) n (%)
Baseline [1]	None	xx (xx.x)	xx (xx.x)	xx (xx.x)	xx (xx.x)	xx (xx.x)	xx (xx.x)
	Trace	xx (xx.x)	xx (xx.x)	xx (xx.x)	xx (xx.x)	xx (xx.x)	xx (xx.x)
	+1	xx (xx.x)	xx (xx.x)	xx (xx.x)	xx (xx.x)	xx (xx.x)	xx (xx.x)
	+2	xx (xx.x)	xx (xx.x)	xx (xx.x)	xx (xx.x)	xx (xx.x)	xx (xx.x)
	+3	xx (xx.x)	xx (xx.x)	xx (xx.x)	xx (xx.x)	xx (xx.x)	xx (xx.x)
	+4	xx (xx.x)	xx (xx.x)	xx (xx.x)	xx (xx.x)	xx (xx.x)	xx (xx.x)
	+5	xx (xx.x)	xx (xx.x)	xx (xx.x)	xx (xx.x)	xx (xx.x)	xx (xx.x)
	No Result	xx (xx.x)	xx (xx.x)	xx (xx.x)	xx (xx.x)	xx (xx.x)	xx (xx.x)
Day 7	Not Done	xx (xx.x)	xx (xx.x)	xx (xx.x)	xx (xx.x)	xx (xx.x)	xx (xx.x)
	None	xx (xx.x)	xx (xx.x)	xx (xx.x)	xx (xx.x)	xx (xx.x)	xx (xx.x)
	Trace	xx (xx.x)	xx (xx.x)	xx (xx.x)	xx (xx.x)	xx (xx.x)	xx (xx.x)
	+1	xx (xx.x)	xx (xx.x)	xx (xx.x)	xx (xx.x)	xx (xx.x)	xx (xx.x)
	+2	xx (xx.x)	xx (xx.x)	xx (xx.x)	xx (xx.x)	xx (xx.x)	xx (xx.x)
	+3	xx (xx.x)	xx (xx.x)	xx (xx.x)	xx (xx.x)	xx (xx.x)	xx (xx.x)
	+4	xx (xx.x)	xx (xx.x)	xx (xx.x)	xx (xx.x)	xx (xx.x)	xx (xx.x)
	+5	xx (xx.x)	xx (xx.x)	xx (xx.x)	xx (xx.x)	xx (xx.x)	xx (xx.x)
Continue for other visits	No Result	xx (xx.x)	xx (xx.x)	xx (xx.x)	xx (xx.x)	xx (xx.x)	xx (xx.x)
	Not Done	xx (xx.x)	xx (xx.x)	xx (xx.x)	xx (xx.x)	xx (xx.x)	xx (xx.x)

[1] Baseline = Screening (Day -28 to Day -15); N = Number of safety subjects; n = Number of subjects with data in the summarized category;  
 NEG (negative) = not present or none seen; +(few) = The structure is present but not in all fields examined, a specific structure is occasionally found in a field;  
 ++(moderate) = The structure is present in all fields examined but quantification is still low; +++;(many) = The structure is present in all fields examined.  
 Percentages are based on the number of subjects with a non-missing measurement for that variable in each corresponding visit.

Program location/program name.sas/ddmmmyyyy/hh:mm  
Source Data: Listing xxxxxxx Database Extract Date: ddmmmyyyy

---

Programming notes:

Parameter = Color, appearance, pH, Microscopy, Specific gravity, Glucose,  
Protein, Ketones, Blood, Billirubin, Leukocyte Esterase, Nitrite

---

Table 14.3.5.4  
 Summary of Laboratory Results - Liver Function Test Elevation and Hy's Law Criteria Summary

Safety Set

Elevation Criteria	GSP304				Spiriva R		
	(N=xxx) n (%)	(N=xxx) n (%)	(N=xxx) n (%)	Total (N=xxx) n (%)	Placebo (N=xxx) n (%)	5 ug (N=xxx) n (%)	Total (N=xxx) n (%)
Hy's Law[1]	xx (xx.x)	xx (xx.x)	xx (xx.x)	xx (xx.x)	xx (xx.x)	xx (xx.x)	xx (xx.x)
AST(SGOT)							
2xULN elevations	xx (xx.x)	xx (xx.x)	xx (xx.x)	xx (xx.x)	xx (xx.x)	xx (xx.x)	xx (xx.x)
3xULN elevations	xx (xx.x)	xx (xx.x)	xx (xx.x)	xx (xx.x)	xx (xx.x)	xx (xx.x)	xx (xx.x)
5xULN elevations	xx (xx.x)	xx (xx.x)	xx (xx.x)	xx (xx.x)	xx (xx.x)	xx (xx.x)	xx (xx.x)
10xULN elevations	xx (xx.x)	xx (xx.x)	xx (xx.x)	xx (xx.x)	xx (xx.x)	xx (xx.x)	xx (xx.x)
ALT(SGPT)							
2xULN elevations	xx (xx.x)	xx (xx.x)	xx (xx.x)	xx (xx.x)	xx (xx.x)	xx (xx.x)	xx (xx.x)
3xULN elevations	xx (xx.x)	xx (xx.x)	xx (xx.x)	xx (xx.x)	xx (xx.x)	xx (xx.x)	xx (xx.x)
5xULN elevations	xx (xx.x)	xx (xx.x)	xx (xx.x)	xx (xx.x)	xx (xx.x)	xx (xx.x)	xx (xx.x)
10xULN elevations	xx (xx.x)	xx (xx.x)	xx (xx.x)	xx (xx.x)	xx (xx.x)	xx (xx.x)	xx (xx.x)
Gamma-glutamyl transferase							
2xULN elevations	xx (xx.x)	xx (xx.x)	xx (xx.x)	xx (xx.x)	xx (xx.x)	xx (xx.x)	xx (xx.x)
3xULN elevations	xx (xx.x)	xx (xx.x)	xx (xx.x)	xx (xx.x)	xx (xx.x)	xx (xx.x)	xx (xx.x)
5xULN elevations	xx (xx.x)	xx (xx.x)	xx (xx.x)	xx (xx.x)	xx (xx.x)	xx (xx.x)	xx (xx.x)
10xULN elevations	xx (xx.x)	xx (xx.x)	xx (xx.x)	xx (xx.x)	xx (xx.x)	xx (xx.x)	xx (xx.x)
Alkaline Phosphatase							
2xULN elevations	xx (xx.x)	xx (xx.x)	xx (xx.x)	xx (xx.x)	xx (xx.x)	xx (xx.x)	xx (xx.x)
3xULN elevations	xx (xx.x)	xx (xx.x)	xx (xx.x)	xx (xx.x)	xx (xx.x)	xx (xx.x)	xx (xx.x)
5xULN elevations	xx (xx.x)	xx (xx.x)	xx (xx.x)	xx (xx.x)	xx (xx.x)	xx (xx.x)	xx (xx.x)
10xULN elevations	xx (xx.x)	xx (xx.x)	xx (xx.x)	xx (xx.x)	xx (xx.x)	xx (xx.x)	xx (xx.x)
Total Bilirubin							
2xULN elevations	xx (xx.x)	xx (xx.x)	xx (xx.x)	xx (xx.x)	xx (xx.x)	xx (xx.x)	xx (xx.x)
3xULN elevations	xx (xx.x)	xx (xx.x)	xx (xx.x)	xx (xx.x)	xx (xx.x)	xx (xx.x)	xx (xx.x)
5xULN elevations	xx (xx.x)	xx (xx.x)	xx (xx.x)	xx (xx.x)	xx (xx.x)	xx (xx.x)	xx (xx.x)
10xULN elevations	xx (xx.x)	xx (xx.x)	xx (xx.x)	xx (xx.x)	xx (xx.x)	xx (xx.x)	xx (xx.x)

Direct Bilirubin

2xULN elevations	xx (xx.x)						
3xULN elevations	xx (xx.x)						
5xULN elevations	xx (xx.x)						
10xULN elevations	xx (xx.x)						

---

[1] Hy's Law criteria are based on the following:  $\geq 2$  x ULN elevation of Bilirubin and 3 x ULN elevation of either ALT or AST. In order to meet the above criteria, a subject must experience the elevation in bilirubin and ALT or AST at the same visit. N = Number of safety subjects; n = Number of subjects with data in the summarized category

Program location/program name.sas/ddmmmyyyy/hh:mm

Source Data: Listing xxxxxxx Database Extract Date: ddmmmyyyy

---

Programming notes:

---

Table 14.3.6.7  
 Summary of Physical Examination by Treatment

Safety Set

Panel/Parameter: <Parameter>

Visit	Category	GSP304				Spiriva R		
		(N=xxx) n (%)	(N=xxx) n (%)	(N=xxx) n (%)	Total (N=xxx) n (%)	Placebo (N=xxx) n (%)	5 ug (N=xxx) n (%)	Total (N=xxx) n (%)
Baseline[1]	n	xxx	xxx	xxx	xxx	xxx	xxx	xxx
	Normal	xx (xx.x)	xx (xx.x)	xx (xx.x)	xx (xx.x)	xx (xx.x)	xx (xx.x)	xx (xx.x)
	Abnormal	xx (xx.x)	xx (xx.x)	xx (xx.x)	xx (xx.x)	xx (xx.x)	xx (xx.x)	xx (xx.x)
	Not Done	xx (xx.x)	xx (xx.x)	xx (xx.x)	xx (xx.x)	xx (xx.x)	xx (xx.x)	xx (xx.x)
Day 7	n	xxx	xxx	xxx	xxx	xxx	xxx	xxx
	Normal	xx (xx.x)	xx (xx.x)	xx (xx.x)	xx (xx.x)	xx (xx.x)	xx (xx.x)	xx (xx.x)
	Abnormal	xx (xx.x)	xx (xx.x)	xx (xx.x)	xx (xx.x)	xx (xx.x)	xx (xx.x)	xx (xx.x)
	Not Done	xx (xx.x)	xx (xx.x)	xx (xx.x)	xx (xx.x)	xx (xx.x)	xx (xx.x)	xx (xx.x)
Continue for other visits								

[1] Baseline = Day -1; N = Number of safety subjects; n = Number of subjects with data in the summarized category  
 Percentages are based on the number of subjects with a non-missing measurement for that variable in each corresponding visit.

Program location/program name.sas/ddmmmyyyy/hh:mm

Source Data: Listing xxxxxxx Database Extract Date: ddmmmyyyy

Programming notes:

Parameter = General Appearance; Skin/subcutaneous Tissue; Head and Neck (including thyroid gland); Eyes, Ears, Nose and Throat; Gastrointestinal System; Lymph Nodes; Musculoskeletal System; Heart/Cardiovascular; Respiratory System; Urogenital System; Ano-rectal; Extremities; Neurological System

Listing 16.2.1.1  
Listing of Subject Disposition

All Screened Subjects

Panel/Treatment Group: <GSP304 [REDACTED]

Site/Subject ID/Sex/Age(years)/Race/Baseline Weight(kg): <xxxx/xxxx/M/25/WHITE/75>

Subject Status	Date of Informed Consent/ Date of Randomization	Date of First Study Medication/ Last Study Medication	Date of Early Termination	Reason for Premature Study Termination
Screen Failure	ddmmmyyyy/ddmmmyyyy	ddmmmyyyy/ddmmmyyyy	ddmmmyyyy	Adverse Event

program location/program name.sas/ddmmmyyyy/hh:mm

---

Programming notes: If the subject status is screen failure, the info past informed consent should show as N/A

---

Listing 16.2.1.2  
Listing of Study Completion/Withdrawal

Safety Set

Site/Subject ID	Treatment	Subject Status	Date of Completion/Withdrawn	Reason for Withdrawn	Study Day
xxxx/xxx-xxxx	xxxx	Complete	ddmmmyyyy/ddmmmyyy	Adverse Event	56

Study day = date of interest – randomization date + 1 if the date of interest occurs on or after the randomization date: Study day = date of interest – randomization date if the date of interest occurs on or before the randomization date

program location/program name.sas/ddmmmyyyy/hh:mm

---

Programming notes:

---

Listing 16.2.1.3  
Listing of Reason for Early Termination

Safety Set

Site/Subject ID	Treatment	Date of Early Termination	Reason for Early Termination	Failed to Inclusion/Exclusion [#]
xxx/xxx-xxxx	xxxx	ddmmmyyyy	Adverse Event	
xxx/xxx-xxxx	xxxx	ddmmmyyyy		Exclusion [2]

program location/program name.sas/ddmmmyyyy/hh:mm

---

Programming notes:

---

Listing 16.2.2  
Protocol Deviations

Full Analysis Set

Site/Subject ID	Subject Status	PD Status	Classification	PD Occur Date	Description	Final Decision	Action to be Taken	BDRM Comment
xxx/xxx-xxxx	Completed	Closed	Inc/Excl Criteria	ddmmmyyyy	xxxx	Major	Exclude from PP	xxxx

PD = Protocol Deviation

program location/program name.sas/ddmmmyyyy/hh:mm

---

Programming notes:

---

Listing 16.2.3  
Listing of Subjects in Analysis Population

Full Analysis Set

Site/Subject ID	FAS-Exclusion FAS Reason	SAF Exclusion SAF Reason	PP-Exclusion PP Reason	PKAS-Exclusion PKAS Reason	Completed Study	Latest Visit	Protocol Deviation
xxxxxx	xxx xxx	xxx xxx	xxx xxx	xxx xxx	xxx	xxx	xxx

FAS = Full Analysis Set; SAF = Safety Set; PP = Per-Protocol Set; PKAS = Pharmacokinetic Set

FAS will include all subjects who are randomized, have received at least 1 dose of study medication and have at least 1 post-baseline PD assessment; SAF will include all subjects who are randomized and received at least 1 dose of study medication; PP will include all subjects who are randomized, received at least 1 dose of study medication, completed the study and do not have any major protocol deviations; PKAS will include all subjects who are randomized, received at least 1 dose of study treatment and have at least 1 quantifiable PK sample and do not have any major protocol deviations.

program location/program name.sas/ddmmmyyyy/hh:mm

---

Programming notes:

---

Listing 16.2.4.1  
Listing of Demographic and Baseline Characteristics

Safety Set

Panel/Site/Subject ID/Treatment/Age/Sex/Race/Ethnicity: <xxx/xx-xxxx/Placebo/45/F/Other/WHITE >

---

Height(cm)	Weight(kg)	BMI(kg/m  )	Smoking Status (Y/N)	X-Ray Interpretation screening? (Y/N) [1]	Any COPD exacerbation in previous 3 months before	If [1] =Yes, COPD Hospitalization? (Y/N)
xxx	xxx	xxx	Y	xxxx	xxxx	xxxx

Y =Yes; N =No; ANCS = Abnormal, not clinically significant; ACS = Abnormal, clinically significant; UE = Un-evaluable  
program location/program name.sas/ddmmmyyyy/hh:mm

---

Programming notes:

---

Listing 16.2.4.2  
Listing for Medical History

Safety Set

Site/Subject ID	Body System	Medical History Term	LLT/LLT Code	PT/PT Code	HLT	HLT Code	HLGT/HLGT Code	SOC/SOC code
xxxx	xxxx	xxxx	xxx/xxx	xxx/xxx	xxx/xxx	xxx/xxx	xxx/xxx	xxx/xxx

MH = Medical History; LLT = Lowest Term; PT = Preferred Term; HLT = High Level Term; HLGt = High Level Group Term; SOC = System Organ Class  
program location/program name.sas/ddmmmyyyy/hh:mm

---

Programming notes:

---

Listing 16.2.5.1  
Listing of Exposure to Study Medication

Safety Set

Site/Subject ID	Treatment	Date of First Dose	Date of Last Dose	Study Medication Duration (days)
xxx/xxx-xxxx	GSP304 [REDACTED]	ddmmmyyyy	ddmmmyyyy	42

Duration = Last dose date – First dose date +1

program location/program name.sas/ddmmmyyyy/hh:mm

---

Programming notes:

---

Listing 16.2.5.2  
Listing of Treatment Compliance

Safety Set

Site/Subject ID	Treatment	Number of Received/Number of Expected	Compliance (%)
xxx/xxx-xxxx	Placebo	9/9	100%

program location/program name.sas/ddmmmyyyy/hh:mm

---

Programming notes:

---

Listing 16.2.5.3  
Listing of Average Daily Dose and Nebulization Time

Safety Set

Site/Subject ID	Visit	Treatment	Average Daily Dose (ug)	Nebulization Time in Miniute
xxx-xxxx	xxxxx	GSP304 [REDACTED]	xxxx	xxx

program location/program name.sas/ddmmmyyyy/hh:mm

---

Programming notes:

---

Listing 16.2.5.4  
Listing for Prior/Concomitant Medication per Subject

Safety Set

Panel/Site/Subject ID/Sex/Age(years)/Race/Baseline Weight(kg): <xxxx/M/25/WHITE/75>

Treatment	Drug Class/Preferred Term/Medication Reported	Flag	Start Date/End Date	Study Day Start/End	On-going	Dose	Unit	Route	Frequency	Indication
Placebo	xxxxxx/xxxx/xxxx	P/C	Ddmmmyyyy/ddmmmyyyy	12/15	Y	xxx	xxxx	xxx	xxxx	xxxx

Study day = date of interest – randomization date + 1 if the date of interest occurs on or after the randomization date: Study day = date of interest – randomization date if the date of interest occurs on or before the randomization date;

Prior and concomitant medications were coded with the WHO Drug dictionary dated September, 2015; Flag: P = Prior medication if both the start and stop date exist and are before the first dose date of study drug , C = Concomitant medication if the start date is on or after the first dose date of study drug, P/C = if the start date is before the first dose date of study drug and the stop date is after the first dose date of study drug or the medication is continuing,

program location/program name.sas/ddmmmyyyy/hh:mm

---

Programming notes:

---

Listing 16.2.5.5  
Listing of Study Subjects – Unblinding

Safety Set

Site/Subject ID	Randomization Number	Randomization Date	Treatment Randomized	Treatment Received
xxxx/xxx-xxxx	xxxxxx	ddmmmyyyy	GSP304 [REDACTED]	GSP304 [REDACTED]

program location/program name.sas/ddmmmyyyy/hh:mm

---

Programming notes:

---

Listing 16.2.5.6  
Listing of Rescue Medication per Subject

Safety Set

Panel/Site/Subject ID/Sex/Age(years)/Race/Baseline Weight(kg): <xxxx/M/25/WHITE/75>

Treatment	Medication Reported
Placebo	xxxx

Rescue medications were collected on patient eDiaries.

program location/program name.sas/ddmmmyyyy/hh:mm

Note To Programmer: List data as collected/ reported from eDiary. Add columns based on data collected.

Listing 16.2.6.1

Listing of Change from Baseline in Primary and Secondary Pharmacodynamics Endpoints

Safety Set

Panel/Site/Subject ID/Sex/Age(years)/Race/Baseline Weight(kg): <xxxx/M/25/WHITE/75>

Treatment	Endpoints	Value at Baseline	Value at Day 1/Day 21	Change from Baseline at Day 1/Day 21
GSP304 [REDACTED]	[1]	xxxx	xxxx/xxx	xxxxx /xxx

[1] Primary Endpoint: Change from baseline in trough FEV1 at 24 hours after the last dose of treatment on Day 21

[2] Secondary Endpoint: Change from baseline in peak FEV1 within 12 hours post dose on Day 1 and Day 21

[3] Secondary Endpoint: Change from baseline in FVC on Day 1 and Day 21

[4] Secondary Endpoint: Change from baseline in time-normalized area under the curve for FEV1 measured over 12 hours on Day 1 and Day 21

program location/program name.sas/ddmmmyyyy/hh:mm

---

Programming notes:

---

Listing 16.2.6.2.1  
Listing of Plasma Concentrations

PK Analysis Set

Site/Subject ID	Treatment	Visit	Sample Collection Date	Hour	Nominal Time	Actual Time	Deviations Time	Plasma Concentration (unit)	Comment
xx/xxxx	xxx	xxx	ddmmmyyyy	Pre-dose	xxxx	xxx	xxxx	xxxx	xxxxx

Lower Limit of Quantification (LLOQ) = XX:XX (unit); BLQ = Below the Limit of Quantification; NA = Not Applicable; NS = Not Sampled

program location/program name.sas/ddmmmyyyy/hh:mm

---

Programming notes: Add comment if sample collected outside of allowed window (reason) and or reason sample excluded

---

Listing 16.2.6.2.2  
Listing of Urine Concentrations on Day1 and Day 21

PK Analysis Set

Panel/ Site/Subject ID /Visit/Study Day: <Day 1/12 >

Treatment	Last Dose Date/Time	Scheduled Time(unit)	Sample Date/Time(start)	Sample Date/Time(end)	Concentration (unit)	Volumne (unit)	Comment
GSP304 [REDACTED]	ddmmmyyyy/hh:mm	hh:mm(sec)	ddmmmyyyy/hh:mm	ddmmmyyyy/hh:mm	xxxx	xxxx	xxxx

Study day = date of interest – randomization date + 1 if the date of interest occurs on or after the randomization date: Study day = date of interest – randomization date if the date of interest occurs on or before the randomization date

Lower Limit of Quantification (LLOQ) = XX (pg/mL); BLQ = Below the Limit of Quantification; NA = Not Applicable; NS = Not Sampled

program location/program name.sas/ddmmmyyyy/hh:mm

---

Programming notes: Add comment if sample collected outside of allowed window and or reason sample excluded

---

Listing 16.2.6.2.3  
Listing of Pharmacokinetic Parameters

PK Analysis Set

Panel/ Site/Subject ID/Sex/Age(years)/Race/Baseline Weight(kg): <xxxx/xxx-xxx//M/25/WHITE/75>

Treatment	Visit	Hour	Parameter(unit)	Value	Comment
GSP304 [REDACTED]	Day 1	Pre-dose	AUC(ng.h/mL)	xxx	xxxxx

program location/program name.sas/ddmmmyyyy/hh:mm

---

Programming notes: Add comment if sample collected outside of allowed window and or reason sample excluded

Include all PK parameters

---

Listing 16.2.6.2.4

Listing of Pharmacokinetic Parameters Excluded from Analysis

PK Analysis Set

Site/Subject ID	Treatment	Visit	Sequence	Period	Parameter(unit)	Value	Reason
xxx-xxxx	GSP304 [REDACTED]	xxx	xxxxx	xxxx	AUC(ng.h/mL)	xxx	Not be determined

program location/program name.sas/ddmmmyyyy/hh:mm

---

Programming notes:

---

Listing 16.2.7.1  
Listing of Treatment Emergent Adverse Events

Safety Set

Panel/Site/Subject ID/Treatment/AE/Stat Date/End Date/Study Day/Ongoing: <xxxx/xxxx/xxx/xxx/Y/ddmmmyyyy/ddmmmyyyy/xx/Y>

Severity	SAE? Reasons	SAE- Seriousness	Relationship to Study Medication	Action Taken with IP	Outcome	LLT/LLT Code	PT/PT Code	HLT	HLT Code	HLGT/HLGT Code	SOC/SOC code
xxxx	Y	death	xxxx	xxxx	xxxx	xxxx/xxxx	xxxx/xxxx	xxxx/xxxx	xxxx/xxxx	xxxx/xxxx	xxxx/xxxx

Treatment Emergent AEs are defined as AEs (identified by PT) that begins or that worsens in severity after at least one dose of study treatment has been administered, up to the last study visit; AE = Adverse Events; SAE = Serious Adverse Event; LLT = Lowest Term; PT = Preferred Term; HLT = High Level Term; HLGT = High Level Group Term; SOC = System Organ Class; AEs were coded using MedDRA v19.1; Study day = date of interest – randomization date + 1; Treatment Emergent AEs are defined as AEs (identified by PT) that begins or that worsens in severity after at least one dose of study treatment has been administered, up to the last study visit; PT = Preferred Term

program location/program name.sas/ddmmmyyyy/hh:mm

---

Programming notes:

Repeat for

Table 16.2.7.2 Listing of Pre-Treatment Adverse Events

All Screened Subjects

Footnote: Pre-Treatment AEs (PTAEs) are defined as AEs (identified by PT) that begin or that worsen in severity between study Day -14 and study drug administration, and last up to the AE stop date

---

Listing 16.2.7.3  
Listing of Serious Adverse Events

All Screened Subjects

Panel/Site/Subject ID/Treatment/AE/Stat Date/End Date/Study Day/Ongoing: <xxxx/xxxx/xxx/xxx/xxx/Y/ddmmmyyyy/ddmmmyyyy/xx/Y >

Severity	SAE-Seriousness Reasons	Relationship to Study Medication	Action Taken with IP	Outcome	LLT/LLT Code	PT/PT Code	HLT	HLT Code	HLGT/HLGT Code	SOC/SOC code
xxxx	death	xxxx	xxxx	xxxx	xxxx/xxxx	xxxx/xxxx	xxxx/xxxx	xxxx/xxxx	xxxx/xxxx	xxxx/xxxx

Treatment Emergent AEs are defined as AEs (identified by PT) that begins or that worsens in severity after at least one dose of study treatment has been administered, up to the last study visit; SAE = Serious Adverse Event; LLT = Lowest Term; PT = Preferred Term; HLT = High Level Term; HLGT = High Level Group Term; SOC = System Organ Class; AEs were coded using MedDRA v19.1; Study day = date of interest – randomization date + 1; Treatment Emergent AEs are defined as AEs (identified by PT) that begins or that worsens in severity after at least one dose of study treatment has been administered, up to the last study visit; PT = Preferred Term

program location/program name.sas/ddmmmyyyy/hh:mm

Listing 16.2.8.1  
Listing of Laboratory Results per Subject - Biochemistry

Safety Set

Panel/Site/Subject ID/Sex/Age(years)/Race/Baseline Weight(kg): <xxxx/M/25/WHITE/75>

Treatment Parameter(unit)	Normal Range	Day number	Lab Not Done (Y/N)	Scheduled Visit (Y/N)	Data Sample Taken	Lab Result [1]	Change from Baseline [2]
Placebo	Basophil(10  /L) xxx-xxx	Day 1	N	Y	ddmmmyyyy	0.2 N	0.06

[1] N = Normal; ANCS = Abnormal, not clinically significant; ACS = Abnormal, clinically significant; UE = Unevaluable; NA = Not Applicable

[2] Baseline = Screening (Day -28 to Day -15)

program location/program name.sas/ddmmmyyyy/hh:mm

---

Programming notes:

Repeat for

Listing 16.2.8.2 Listing of Laboratory Results per Subject - Hematology

Footnote:

[1] N = Normal; ANCS = Abnormal, not clinically significant; ACS = Abnormal, clinically significant; UE = Unevaluable; NA = Not Applicable

[2] Baseline = Screening (Day -28 to Day -15)

Listing 16.2.8.3 Listing of Laboratory Results per Subject – Urinalysis

Footnote:

[1] N = Normal; ANCS = Abnormal, not clinically significant; ACS = Abnormal, clinically significant; UE = Unevaluable; NA = Not Applicable

[2] Baseline = Screening (Day -28 to Day -15)

NEG(negative) = not present or none seen; +(few) = The structure is present but not in all fields examined. A specific structure is occasionally found in a field; ++(moderate) = The structure is present in all fields examined but quantification is still low.; +++;(many) = The structure is present in all fields examined.

---

Listing 16.2.8.4  
Listing of Test Results

Safety Set

Site/Subject ID	Visit	Test	Done?	Results
xxx/xxxxxx	Screening	Pregnancy/xxxx/xxx	Yes	xxxx

program location/program name.sas/ddmmmyyyy/hh:mm

---

Programming notes: Test = Chest XRay, CT Scan, FSH test and Serum Pregnancy Test, Blood Alcohol Test, Urinalysis, Serology Test  
Thyroid stimulating hormone; Follicle stimulating hormone; HBsAg and HCV antibody;  
The list should be ordered by Site/Subject ID, then Visit

---

Listing 16.2.9.1  
Listing of Vital Signs Data per Subject

Safety Set

Subject ID/Sex/Age(years)/Race/Baseline Weight(kg): <xxxx/M/25/WHITE/75>

Treatment	Visit	Scheduled Visit (Y/N)	Date	Parameter(unit)	Result	Abnormality	Clinically Significant?
Placebo	Screening	xxxx	ddmmmyyyy	Heart Rate (bpm)	xxxx	No	No

program location/program name.sas/ddmmmyyyy/hh:mm

---

Programming notes:

Repeat for

Listing 16.2.9.2 Listing of 12-Lead ECG Measurement per Subject

Listing 16.2.9.3 Listing of Physical Examinations per Subject

---

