#### **10.4. Laboratory Data**

Baseline and post-baseline clinical laboratory data (hematology, biochemistry, liver function, and urinalysis), will be summarized for Visit 4 to Visit 7 (the Final Visit). Descriptive statistics (number of subjects, mean, SD, median, minimum and maximum) will be presented for laboratory data as well as change from baseline by treatment and visit. In addition, values outside the respective normal range and values deemed as clinically significant by the Investigator will be listed.

The number of subjects with values of potential clinical significance determined by the investigator will be tabulated by treatment group and visit.

Shift tables will present changes from baseline in laboratory data (categorized as normal; abnormal, not clinically significant; and abnormal, clinically significant) to end of treatment.

All laboratory data will be listed by treatment and subject.

Estimated Glomerular filtration rate (eGFR) will be estimated using the Cockcroft-Gault approach.

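### The laboratory shift table reports Day 21 status, but its programming note tells the programmer to use the worst post-baseline category

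*SAP*

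**What the plan says.** Section 12.2 gives the shell of Table 14.3.5.1.2 under the title "Shift Summary from Baseline to Day 21 in Biochemistry". Its result columns stand under the header "Subject Status at Day 21", and every cell is n over N3, where N3 is "Number of safety subjects with baseline and Day 21 data". Footnote [2] adds: "Percentages are based on total subjects with baseline and Day 21 data". Footnotes [3] and [4] apply the same Day 21 condition within each baseline category.

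Section 10.4 agrees on the time point. It says "Shift tables will present changes from baseline in laboratory data", lists the categories, and closes with "abnormal, clinically significant) to end of treatment".

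The programming notes under the same shell say something else. Each subject is to be counted once per parameter, "in the maximum post-baseline severity, for that laboratory parameter". The next sentence reads: "Subjects without any post-baseline results are not included in the shift summary". Neither mentions Day 21 or end of treatment.

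The shell is then repeated for hematology, urinalysis, vital signs and ECG, each with a Day 21 title. No replacement for the notes is given.

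**The concern.** A programmer working from this shell has two rules for one table. The title, header and footnotes ask for the Day 21 category among subjects with Day 21 data. The note asks for the worst category at any post-baseline visit, and sets its only exclusion by reference to any post-baseline result.

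If the note is followed, a subject who is abnormal at Day 7 and normal at Day 21 is printed as abnormal at Day 21. The same could happen to a subject whose only abnormality is at the Day 35 follow-up, two weeks after the last dose. Safety and tolerability are the secondary objective of the study (section 3.1.2), and laboratory parameters and vital signs are named safety endpoints (section 3.2.3). A reader of the finished table could not tell Day 21 status from a transient or off-treatment finding.

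**Working it through.** The SAP states no figure for these tables, so there is none to reproduce. The check compares the two rules and then sizes the difference under assumptions.

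**Visits in play (section 4.5)**
- Hematology, biochemistry and urinalysis: Days 7, 14, 21 and 35 after the screening baseline, so four scheduled post-baseline visits. Section 10.4 summarizes Visits 4 to 7, which includes follow-up.
- Vital signs: several post-baseline readings, among them Days 7, 14, 20, 21, 22 and 35.
- ECG: Day 21 pre-dose only. Section 6.7.5 keeps unscheduled readings out of summaries.

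**The two rules side by side**

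| Element | Title, header, N3, footnotes | Programming notes |
|---|---|---|
| Category counted | Day 21 | Worst post-baseline |
| Subjects | Baseline and Day 21 data | Only those with no post-baseline result are left out |
| Visits | Day 21 | Not limited |

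**Direction.** The worst category over a set of visits that includes Day 21 cannot be milder than the Day 21 category. Among subjects with Day 21 data, the note therefore gives an abnormality rate equal to or above the Day 21 rate.

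**Size (assumed inputs).** Let p be the chance of an abnormal result at any one visit and k the number of visits. For independent visits, P(abnormal at least once) = 1 − (1 − p)^k. With p = 10% and k = 4 this is 1 − 0.9^4 = 1 − 0.6561 = 34.4%. For correlated visits, an exchangeable latent normal model was simulated. At full correlation the answer is p itself.

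| Assumed p per visit | Independent | Correlation 0.5 | Correlation 0.8 | Full correlation |
|---|---|---|---|---|
| 5%, four visits | 18.5% | 14.4% | 10.6% | 5% |
| 10%, four visits | 34.4% | 25.9% | 19.2% | 10% |
| 20%, four visits | 59.0% | 44.4% | 34.3% | 20% |
| 10%, three visits (Day 35 not counted) | 27.1% | 21.8% | 17.2% | 10% |

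Under the Day 21 rule each row would simply show p. The figures apply to the Total row; rows conditional on baseline category would differ. For ECG, k = 1 and both rules give p.

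**Denominator.** Section 4.3.1 plans 31 randomized and 28 evaluable subjects per arm. Suppose the 3 others all have an earlier laboratory result but none at Day 21. If they are counted while N3 stays at 28, the Total row could sum to 31/28 = 110.7%. This is an upper bound on one reading of the notes.

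**The case against.** The strongest reply is that almost everything in the shell points to Day 21: title, header, N2, N3 and three footnotes, supported by the display list in section 12.1 and by section 10.4. A programmer who follows those produces a correct table. A reader might infer that the plan will overstate Day 21 abnormality as a matter of course. The SAP does not support that, because the overstatement arises only if the note is followed. What stands is that the note is the explicit instruction to the programmer and contradicts the rest, so one of them must change.

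The numerator mismatch is likewise a possible reading. The second note sentence is an exclusion; it does not say that everyone else is included, and footnotes [3] and [4] require Day 21 data. Counting Day 35 is also inferred, since the note names no visits.

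A reader might further infer that all the repeated tables are affected. ECG is not, because it has one scheduled post-baseline reading. For vital signs the link is weaker: the note speaks of laboratory parameters and reaches them only through the instruction to repeat the table.

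Finally, these are descriptive tables. Laboratory summaries by visit, tabulations of potentially clinically significant results by visit, and full listings leave Day 21 status visible elsewhere, and the same rule would apply in every arm. That limits the importance of the point but does not remove the contradiction.

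**Conclusion.** The point holds as an internal contradiction in the laboratory shift shell. It covers biochemistry, hematology and urinalysis directly, and vital signs by repetition. The direction of any error is certain among subjects with Day 21 data: equal or upward. Its size is unknown, because the per-visit rate and the within-subject correlation are assumptions and the result runs from no inflation to more than threefold in the 10% illustration. Severity is minor, since the primary endpoints are not touched.

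**What to change.** Delete both programming-note sentences from the shell of Table 14.3.5.1.2: the one on maximum severity and the one on subjects without any post-baseline result. State in their place that the Day 21 value is used with N3 as already defined. This agrees with the title, header, footnotes and section 10.4, and carries through to the repeated tables. The cost is a text edit before programming.

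Optionally, if a worst-value shift is wanted for safety review, give it a separate title, say whether Day 35 counts, and use its own denominator of subjects with baseline and at least one qualifying post-baseline result. That adds one set of tables. Section 10.4 does not require it.
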